4.5.11.4 Confidentiality

Data generated from RCR specimens must be available for inspection upon request by representatives of national and local health authorities, and Roche monitors, representatives, and collaborators, as appropriate.

Patient medical information associated with RCR specimens is confidential and may be disclosed to third parties only as permitted by the Informed Consent Form (or separate authorization for use and disclosure of personal health information) signed by the patient, unless permitted or required by law.

Data derived from RCR specimen analysis on individual patients will generally not be provided to study investigators unless a request for research use is granted. The aggregate results of any research conducted using RCR specimens will be available in accordance with the effective Roche policy on study data publication.

Any inventions and resulting patents, improvements, and/or know-how originating from the use of the RCR data will become and remain the exclusive and unburdened property of Roche, except where agreed otherwise.

4.5.11.5 Consent to Participate in the Roche Clinical Repository

The Informed Consent Form will contain a separate section that addresses participation in the RCR. The investigator or authorized designee will explain to each patient the objectives, methods, and potential hazards of participation in the RCR. Patients will be told that they are free to refuse to participate and may withdraw their specimens at any time and for any reason during the storage period. A separate, specific signature will be required to document a patient's agreement to provide optional RCR specimens. Patients who decline to participate will not provide a separate signature.

The investigator should document whether or not the patient has given consent to participate by completing the RCR Research Sample Informed Consent eCRF.

In the event of an RCR participant's death or loss of competence, the participant's specimens and data will continue to be used as part of the RCR research.

4.5.11.6 Withdrawal from the Roche Clinical Repository

Patients who give consent to provide RCR specimens have the right to withdraw their specimens from the RCR at any time for any reason. *After withdrawal of consent, any*

remaining samples will be destroyed or will no longer be linked to the patient. However, if RBR samples have been tested prior to withdrawal of consent, results from those tests will remain as part of the overall research data. If a patient wishes to withdraw consent to the testing of his or her specimens, the investigator must inform the Medical Monitor in writing of the patient's wishes through use of the RCR Subject Withdrawal Form and, if the trial is ongoing, must enter the date of withdrawal on the RCR Research Sample Withdrawal of Informed Consent eCRF. If a patient wishes to withdraw consent to the testing of his or her RCR samples after closure of the site, the investigator must inform the Sponsor by emailing the study number and patient number to the following email address:

[contact]

A patient's withdrawal from Study GO29665 does not, by itself, constitute withdrawal of specimens from the RCR. Likewise, a patient's withdrawal from the RCR does not constitute withdrawal from Study GO29665.

4.5.11.7 Monitoring and Oversight

RCR specimens will be tracked in a manner consistent with Good Clinical Practice by a quality-controlled, auditable, and appropriately validated laboratory information management system, to ensure compliance with data confidentiality as well as adherence to authorized use of specimens as specified in this protocol and in the Informed Consent Form. Roche monitors and auditors will have direct access to appropriate parts of records relating to patient participation in the RCR for the purposes of verifying the data provided to Roche. The site will permit monitoring, audits, IRB/EC review, and health authority inspections by providing direct access to source data and documents related to the RCR samples.

4.6 PATIENT, TREATMENT, STUDY, AND SITE DISCONTINUATION

4.6.1 Patient Discontinuation

Patients have the right to voluntarily withdraw from the study (or be withdrawn by their parents or caregivers, if the patient is a minor) at any time for any reason. In addition, the investigator has the right to withdraw a patient from the study at any time. Reasons for withdrawal from the study may include, but are not limited to, the following:

- Patient withdrawal of consent (or withdrawal of consent by their parents or caregivers, if the patient is a minor) at any time
- Any medical condition that the investigator or Sponsor determines may jeopardize the patient's safety if he or she continues in the study
- Investigator or Sponsor determines it is in the best interest of the patient
- Patient non-compliance with the study procedures (e.g., dosing instructions, study visits)

Every effort should be made to obtain information on patients who withdraw from the study. The primary reason for withdrawal from the study should be documented on the appropriate eCRF. However, patients will not be followed for any reason after consent has been withdrawn. Patients in the dose-escalation stage who discontinue from the study prior to completing the DLT assessment window for reasons other than a DLT will be replaced except as noted in Section 3.1.1. Patients in the expansion stage who discontinue from the study will not be replaced.

4.6.2 Study Drug Discontinuation

Patients must discontinue study drug if they experience any of the following:

- Disease progression as determined by the investigator using mINRC, RANO criteria for HGG, RANO criteria for LGG, or RECIST v1.1, as appropriate. In cases where any doubt regarding disease progression exists, the patient should remain under close observation (e.g., every 4 weeks) and further radiographic assessments should be performed to document either stability or progression. If subsequent evaluations confirm that the patient is experiencing progression, the date of progressive disease should be the time at which the potential progression was first noted. Should such uncertainty occur during the treatment period, the patient may continue with the study treatment until the next scheduled efficacy assessment.
- Unacceptable toxicity despite per-protocol dose reductions or treatment interruptions
- Pregnancy
- Withdrawal of consent

Patients who discontinue study drug for any reason will be asked to return to the clinic for a study drug discontinuation visit and undergo follow-up assessments (see the schedule of assessments in [Appendix 1](#)). If treatment with another anti-cancer treatment is scheduled to begin less than 30 days after the last dose of cobimetinib, assessments at this visit should be performed before the patient starts the other treatment, if possible. Patients who discontinue for reasons other than progressive disease should continue follow-up assessments, including tumor assessments, using the same schedule of assessments as on treatment until radiographic documentation of progressive disease, start of another treatment, or withdrawal of consent. The primary reason for study drug discontinuation should be documented on the appropriate eCRF. Patients in the dose-escalation stage who discontinue study drug prior to completing the DLT assessment window for reasons other than a DLT will be replaced except as noted in Section 3.1.1. Patients in the expansion stage who discontinue study drug will not be replaced.

4.6.3 Study and Site Discontinuation

The Sponsor has the right to terminate this study at any time. Reasons for terminating the study may include, but are not limited to, the following:

- The incidence or severity of adverse events in this or other studies indicates a potential health hazard to patients.
- Patient enrollment is unsatisfactory.

The Sponsor will notify the investigator if the study is discontinued.

The Sponsor has the right to close a site at any time. Reasons for closing a site may include, but are not limited to, the following:

- Excessively slow recruitment
- Poor protocol adherence
- Inaccurate or incomplete data recording
- Non-compliance with the International Conference on Harmonisation (ICH) guideline for Good Clinical Practice
- No study activity (i.e., all patients have completed and all obligations have been fulfilled)

5. ASSESSMENT OF SAFETY

5.1 SAFETY PLAN

The safety plan for patients in this study is based on clinical experience with cobimetinib in completed and ongoing studies. The anticipated important safety risks of cobimetinib are outlined below. Please refer to the cobimetinib Investigator's Brochure for a complete summary of safety information.

Several measures will be taken to ensure the safety of patients participating in this trial. Eligibility criteria have been designed to exclude patients at higher risk for toxicities (see Section 4.1). In addition, patients will undergo safety monitoring during the study as described in Section 4.5, Section 5, and the schedule of assessments (see Appendix 1).

An Internal Monitoring Committee and an Scientific Oversight Committee will monitor patient safety throughout the study. The Internal Monitoring Committee will provide a recommendation on the dose to be taken forward into the expansion stage after completion of the dose-escalation stage (see Section 3.1.3 for details).

Finally, guidelines for managing adverse events, including criteria for dosage modification and treatment interruption or discontinuation, have been provided (see Section 5.1.1). These guidelines apply to patients in the dose-escalation and expansion stages. However, the guidelines are not intended to replace clinical judgment or dictate care of individual patients.

5.1.1 Management of Specific Adverse Events

Guidelines for managing specific adverse events are provided in [Table 2](#). Asymptomatic declines in left ventricular ejection fraction should be managed according to the algorithm presented in [Table 3](#) in Section [5.1.2.1](#).

If dose reduction is indicated for an individual patient, the dose should be reduced to the next lower dose level, with dose defined in [Appendix 10](#). The dose regimen of adult patients (≥ 18 years of age) treated with the adult-recommended daily dose of 60 mg will be reduced by one 20 mg tablet (i.e., from 60 mg to 40 mg). If the patient is treated at the lowest defined dose level, the dose should be reduced by 25%. Note that the need for dose reduction below the minimum doses for administration in this study (specified in [Appendix 10](#)) is considered unacceptable toxicity and requires study drug discontinuation. For patients taking tablets, study drug should be discontinued if required weekly dose after reduction is < 60 mg/week. For patients taking suspension, study drug should be discontinued if required dose after reduction is < 4.8 mg (1 mL) daily. Dose re-escalation is not allowed.

Table 2 Guidelines for Management of Specific Adverse Events

Event	Action to Be Taken

Grade ≥ 2 diarrhea
	
Grade ≥ 3 diarrhea
 
 • If Grade ≥ 3 diarrhea occurs despite adequate supportive care, do not administer cobimetinib until recovery to Grade ≤ 1. • Following recovery, resume cobimetinib at a dose corresponding to a reduction of one dose level. • If patient experiences two episodes of Grade ≥ 3 diarrhea despite adequate supportive care, discontinue cobimetinib permanently. 
Grade 2 diarrhea
 
 • If Grade 2 diarrhea persists for ≥ 10 days despite adequate supportive care, do not administer cobimetinib until recovery to Grade ≤ 1. • Following recovery, resume cobimetinib at a reduced dose after consulting with the Medical Monitor.

Any rash with concurrent signs or symptoms strongly suggestive of a severe Type I hypersensitivity or anaphylactic or anaphylactoid reaction, with painful desquamation or mucosal involvement suggestive of Stevens-Johnson syndrome or toxic epidermal necrolysis, or with other life-threatening complications
	
 • Discontinue cobimetinib permanently. • Immediately consult a dermatologist.

Skin lesion suspicious for SCC/BCC
	
 • Do not administer cobimetinib. • Immediately consult a dermatologist. • Biopsy suspicious lesions. If lesion is benign, resume cobimetinib; if lesion consistent with SCC or BCC, do not resume cobimetinib.

Table 2 Guidelines for Management of Specific Adverse Events (cont.)

Event	Action to Be Taken

Grade ≥ 3 rash that does not meet above criteria
	
 • Consult a dermatologist. • Do not administer cobimetinib until recovery to Grade ≤ 2. • Following recovery, resume cobimetinib at a dose corresponding to a reduction of one dose level. • If patient experiences two episodes of Grade ≥ 3 rash, discontinue cobimetinib. • If Grade ≥ 3 rash persists for > 10 days despite adequate supportive care, discontinue cobimetinib permanently.

Retinopathy or Grade ≥ 2 visual disorders
	
 • Do not administer cobimetinib. • Consult ophthalmologist, who should perform complete ophthalmologic examination that includes visual acuity testing, IOP measurements by tonometry, slit-lamp ophthalmoscopy, indirect ophthalmoscopy with dilation, and SD-OCT. • Resume cobimetinib if no evidence of retinopathy and either visual disorder has recovered to Grade ≤ 1 or visual disorder is attributable to underlying disease (i.e., optic glioma). 
Diagnosis of serous retinopathy
 
 • Do not administer cobimetinib until retinopathy has resolved (or in patients who were symptomatic at presentation, recovered to Grade ≤ 1). • When retinopathy resolves, resume cobimetinib at the next lower dose per the dose-escalation scheme, or if at or below lowest dose level, reduce dose by 25% (Section 3.1.1.2). • If retinopathy recurs, discontinue cobimetinib permanently. 
Diagnosis of retinal vein occlusion or Grade 3+ retinal detachment
 
 • Permanently discontinue cobimetinib

Grade ≥ 3 ALT or AST elevations
	
ALT or AST elevation of $\geq 5 \times$ ULN
 
 • Do not administer cobimetinib until recovery to $< 3 \times$ ULN. • Following recovery, resume cobimetinib at a dose corresponding to a reduction of one dose level. 
ALT or AST $> 3 \times$ ULN in combination with total bilirubin $> 2 \times$ ULN or clinical jaundice
 
 • Discontinue cobimetinib permanently.

Table 2 Guidelines for Management of Specific Adverse Events (cont.)

Event	Action to Be Taken
Grade ≥ 3 rash that does not meet above criteria	
 • Consult a dermatologist. • Do not administer cobimetinib until recovery to Grade ≤ 2. • Following recovery, resume cobimetinib at a dose corresponding to a reduction of one dose level. • If patient experiences two episodes of Grade ≥ 3 rash, discontinue cobimetinib. • If Grade ≥ 3 rash persists for > 10 days despite adequate supportive care, discontinue cobimetinib permanently.
Left ventricular dysfunction Symptomatic congestive heart failure Asymptomatic LVEF decrease	
 • Discontinue cobimetinib permanently. • Consult algorithm Table 3 in Section 5.1.2.1. • Patients who require dose reduction should have LVEF measurements at 2, 4, 10, and 16 weeks after diagnosis or as clinically indicated.
Cerebral hemorrhage (all grades) Grade 2 hemorrhage (excluding cerebral hemorrhage) Grade ≥ 3 hemorrhage	
 • Permanently discontinue cobimetinib. • Interrupt cobimetinib treatment until recovery to Grade ≤ 1, then contact Medical Monitor prior to restarting. Do not resume cobimetinib without approval of Medical Monitor and careful benefit-risk assessment. • There are no data on the effectiveness of cobimetinib dose modification for hemorrhage events. Clinical judgment should be applied when considering restarting cobimetinib treatment. • Permanently discontinue cobimetinib.
Rhabdomyolysis and CPK elevations Rhabdomyolysis or symptomatic CPK elevations	
 • Interrupt cobimetinib treatment. If severity is improved by at least one grade (note rhabdomyolysis can be graded using the scale provided in Table 4 in Section 5.3.3) within 4 weeks, restart cobimetinib at a dose corresponding to a reduction of one dose level, if clinically indicated. If rhabdomyolysis or symptomatic CPK elevations do not improve within 4 weeks, permanently discontinue cobimetinib treatment.

Table 2 Guidelines for Management of Specific Adverse Events (cont.)

Event	Action to Be Taken
Asymptomatic CPK elevations:	
 • Grade ≤3: cobimetinib dosing does not need to be modified or interrupted to manage asymptomatic Grade ≤3 CPK elevations. • Grade 4: Interrupt cobimetinib treatment. If improved to Grade ≤3 within 4 weeks, restart cobimetinib at a dose corresponding to a reduction of one dose level, if clinically indicated. If CPK elevations do not improve to Grade ≤3 within 4 weeks following dose interruption, permanently discontinue cobimetinib treatment.
Other Grade ≥ 3 non-hematologic toxicities or Grade 4 hematologic toxicities considered to be related to cobimetinib	
 • Do not administer cobimetinib until recovery to Grade ≤ 1. • Following recovery, resume cobimetinib at a dose corresponding to a reduction of one dose level. • If patient experiences two episodes of the toxicity, discontinue cobimetinib permanently. • If toxicity persists for > 14 days despite adequate supportive care, discontinue cobimetinib permanently.

BCC=basal cell carcinoma; IOP=intraocular pressure; LVEF=left ventricular ejection fraction; SCC=squamous cell carcinoma; SD-OCT=spectral domain optical coherence tomography; ULN=upper limit of normal.

5.1.2 Risks Associated with Cobimetinib

Information related to risks attributed to cobimetinib is based on safety data from this Phase III Study GO28141 (cobimetinib plus vemurafenib), Phase Ib Study NO25395 (cobimetinib plus vemurafenib), and Phase I Study MEK4592g (cobimetinib monotherapy). For further information regarding clinical safety, please refer to the current cobimetinib Investigator’s Brochure.

5.1.2.1 Important Identified Risks Associated with Cobimetinib Hemorrhage Events

Hemorrhage including major hemorrhages defined as symptomatic bleeding in a critical area or organ, can occur with cobimetinib. In clinical studies with cobimetinib, events of cerebral hemorrhage, gastrointestinal tract hemorrhage, reproductive tract hemorrhage, and hematuria, have been reported.

In the Phase III Study GO28141, Grade 1–4 hemorrhagic events were reported in 13% of patients treated with cobimetinib plus vemurafenib, and in 7.3% of patients treated with placebo plus vemurafenib. Higher frequencies in the cobimetinib plus vemurafenib arm were observed for cerebral hemorrhage (1% vs. 0%). The majority of hemorrhagic events were Grade 1 or 2 and non-serious. Grade 3 and 4 hemorrhage events were reported in 1.2% of patients receiving cobimetinib plus vemurafenib and 0.8% of patients receiving placebo plus vemurafenib.

Serious and severe bleeding has been reported in both the clinical-trial and postmarketing setting. These events occurred in patients with additional risk factors for bleeding, such as central nervous system metastasis, and/or in patients who use concomitant medications that increased the risk of bleeding (including antiplatelet or anticoagulant therapy). Intracerebral events were predominantly associated with brain metastases in patients on therapy with cobimetinib and vemurafenib for metastatic melanoma.

Caution should be used in patients with additional risk factors for bleeding, such as brain metastases, and/or in patients that use concomitant medications that increase the risk of bleeding (including antiplatelet or anticoagulant therapy).

Instructions for dose modification for hemorrhage events are included in [Table 2](#) in [Section 5.1.1](#).

Any Grade ≥ 2 hemorrhagic event will be considered a dose-limiting toxicity on this study, except intracranial hemorrhagic events, which are considered a dose-limiting toxicity regardless of their grading. For Grade 2 extracranial hemorrhagic events, investigator should not administer study drug until toxicity resolves to Grade ≤ 1 . Dose reductions or discontinuations should be implemented per [Table 2](#) in [Section 5.1.2](#). For hemorrhagic events of Grade ≥ 3 , or for any intracranial hemorrhage, study drug should be permanently discontinued.

Ocular Toxicity (Serous Retinopathy)

Serous retinopathy (fluid accumulation within the layers of the retina is a known adverse drug reaction for cobimetinib (Infante et al. 2012; Schoenberger et al. 2013; Larkin et al. 2014). Manifestations of serous retinopathy include visual disturbances, findings of retinal detachment, and retinopathy. Serous retinopathy events may also be asymptomatic. In Study MEK4592g, visual disturbances associated with accumulation of fluid between the layers of the retina were reported as related to cobimetinib. In some cases, patients had subretinal fluid observed incidentally on ophthalmologic examination without visual symptoms. Some patients have been able to resume cobimetinib at the same dose or at a reduced dose. One dose-limiting toxicity of Grade 3 blurred vision was reported at 125 mg, and all other visual disturbances (including blurred vision and seeing flashing lights) were Grade 1 or 2. Serous retinopathy has been characterized in the Phase III Study GO28141. The study incorporated prospective serial ophthalmic examinations for all enrolled patients. Serous retinopathy was reported more frequently in patients treated with cobimetinib plus vemurafenib than placebo plus vemurafenib (25.5% vs. 2.8%, respectively), and approximately half the events were asymptomatic Grade 1 events. Few patients treated with cobimetinib plus vemurafenib experienced Grade ≥ 3 ocular events (2.8%); the majority of these were managed with dose modification of both cobimetinib and vemurafenib.

To address potential ocular toxicity, all patients are required to undergo a baseline ophthalmologic examination to assess for history or evidence of retinal pathology that is considered to be a risk factor for or indicative of neurosensory retinal detachment, central serous chorioretinopathy, neovascular retinopathy, or retinopathy of prematurity. Patients will also undergo ophthalmologic examinations at specified timepoints throughout the study (see [Appendix 1](#)). Details regarding baseline and subsequent ophthalmologic examinations are provided in Section [4.5.6](#).

Guidelines for management of patients who develop Grade ≥ 2 visual disorders or retinopathy are provided in [Table 2](#) in Section [5.1.1](#).

Cardiac Toxicity

Decrease in cardiac function has been identified as an adverse event that falls under “Warnings and Precautions” for adult use of cobimetinib. Study GO28141 demonstrated a decrease in cardiac function in 7% of cobimetinib plus vemurafenib-treated patients versus 3% of vemurafenib-treated patients. Most cases were asymptomatic. Symptoms consistently improved following treatment discontinuation, treatment interruption, or dose reduction in the cobimetinib arm, while improvement was inconsistent in the vemurafenib arm. There has been no in vitro or nonclinical evidence of decreased cardiac function with cobimetinib administration.

As there is no biomarker that can accurately identify early decreased cardiac function in children, cardiac function will be assessed through echocardiograms performed at specified timepoints throughout the study (see [Appendix 1](#)). This is particularly important in pediatric patients who have been treated with an anthracycline analogue, and even more so in pediatric patients who have had chest radiotherapy in addition to anthracycline treatment, both of which increase the risk of cardiac dysfunction.

Guidelines for the management of symptomatic reduction in left ventricular ejection fraction are provided in [Table 3](#).

Table 3 Guidelines for Management of Asymptomatic Reduction in Left Ventricular Ejection Fraction

Patient	LVEF Value	Recommended Cobimetinib Dose Modification	LVEF Value Following Treatment Break	Recommended Cobimetinib Daily Dose
Asymptomatic	≥ 50% (or 40%–49% and < 10% absolute decrease from baseline)	Continue at current dose	N/A	N/A
	< 40% (or 40%–49% and ≥ 10% absolute decrease from baseline)	Interrupt treatment for 2 weeks	< 10% absolute decrease from baseline	1 st occurrence: reduce by 1 dose level
				2 nd occurrence: reduce by additional dose level
				3 rd occurrence: permanent discontinuation
< 40% (or ≥ 10% absolute decrease from baseline)			Permanent discontinuation	

LVEF=left ventricular ejection fraction; FS=fractional shortening.

Note: Investigators may substitute FS for LVEF in algorithm above as follows:

- FS ≥ 28% equivalent to LVEF 50%
- FS 25%–27.9% equivalent to LVEF 40%–49%
- FS < 25% equivalent to LVEF < 40%

Patients who require dose reduction should have LVEF measurements at 2, 4, 10, and 16 weeks after diagnosis. Patients with symptomatic heart failure must discontinue study drug.

Rhabdomyolysis and CPK Elevations

Elevations in CPK have been observed in patients who received cobimetinib monotherapy as well as when combined with other agents. The majority of CPK elevations reported were asymptomatic, non-serious, and resolved with or without study drug interruption. One event of rhabdomyolysis was reported in the Phase III Study GO28141 (cobimetinib plus vemurafenib), and rhabdomyolysis has been reported in postmarketing experience.

In Study GO28141, elevated CPK was reported as an adverse event more frequently in patients treated with cobimetinib plus vemurafenib (32.4% all grades, 11.3% Grade ≥ 3 events) than placebo plus vemurafenib (8.1% all grades, 0% Grade ≥ 3 events).

CPK will be monitored at baseline, on Cycle 1 Days, 1, 8, 15, and 21; then on Day 1 of each subsequent cycle (monthly), and at study drug discontinuation as indicated in [Appendix 1](#), or as clinically indicated. Instructions for dose modification for elevated CPK and rhabdomyolysis are included in [Table 2](#) in Section [5.1.1](#).

Photosensitivity

No evidence of phototoxicity has been observed with cobimetinib as a single agent. However, photosensitivity was observed on the GO28141 trial with a higher frequency in the cobimetinib plus vemurafenib arm vs. placebo plus vemurafenib arm (46% vs. 35%, respectively). The majority of events were Grades 1 or 2, with Grade ≥ 3 events occurring in 4% of patients in the cobimetinib plus vemurafenib arm versus 0% in the placebo plus vemurafenib arm. There were no apparent trends in the time of onset of Grade ≥ 3 events. Grade ≥ 3 photosensitivity events in the cobimetinib plus vemurafenib arm were treated with primary topical medication in conjunction with interruption of study agents. Grade ≥ 3 photosensitivity on this trial will be treated as any other Grade ≥ 3 non-hematologic toxicity as outlined in [Table 2](#) in Section [5.1.1](#).

Pneumonitis

Events of pneumonitis have been reported in cobimetinib clinical studies. Most reported events were considered non-serious and low-severity grade. In the Phase III Study GO28141, pneumonitis events were reported more frequently in patients treated with cobimetinib plus vemurafenib than placebo plus vemurafenib (1.6% vs. 0.4%, all grades). There were no reported Grade ≥ 3 events in either study arm. Serious events were reported in 2 patients (0.8%) treated with cobimetinib plus vemurafenib. Pneumonitis is an expected adverse drug reaction for cobimetinib.

5.1.2.2 Potential Risks Associated with Cobimetinib Liver Laboratory Abnormalities and Severe Hepatotoxicity

Liver laboratory abnormalities can occur when cobimetinib is used with vemurafenib, and when vemurafenib is used as a single agent.

Liver laboratory test abnormalities, including increases in ALT, AST, and alkaline phosphatase, have been reported as adverse events and serious adverse events in patients treated with cobimetinib plus vemurafenib.

In the Phase III Study GO28141, liver laboratory test abnormalities reported as Grade ≥ 3 adverse events occurred more frequently in patients treated with cobimetinib plus vemurafenib than placebo plus vemurafenib (20.5% vs. 15.1%, respectively).

Generally, elevations in liver laboratory tests were managed effectively with dose modification guidelines. In both study arms, the majority of Grade ≥ 3 liver laboratory test abnormalities resolved.

No Grade ≥ 3 liver laboratory test elevations were reported in the cobimetinib monotherapy Study MEK4952g, with the exception of 1 case of Grade 3 bilirubin increase.

Impaired Female Fertility

There is a potential for effects on fertility and embryo-fetal toxicity based on results from nonclinical studies.

While no dedicated fertility studies have been conducted with cobimetinib in animals, degenerative changes observed in reproductive tissues included increased apoptosis/necrosis of corpora lutea, seminal vesicle and epididymal and vaginal epithelial cells in rats, and epididymal epithelial cells in dogs. These changes were reversible upon discontinuation of cobimetinib administration.

Teratogenicity and Developmental Toxicity

In a dedicated embryo-fetal toxicity study, cobimetinib produced fetal toxicity (resorptions and reductions in fetal weight), and teratogenicity (malformations of the great vessels and skull) at similar systemic exposures to those observed in adult patients administered the 60 mg dose.

See Section 4.1.1 for contraceptive requirements for study.

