Patients who experience a DLT during the assessment window (first 28 days) may not subsequently continue drug at full dose, even if the drug is withheld until resolution of the toxic event. The investigator should use guidance in Section 5.1.1 and Table 2 (and if guidance is not specified, investigator discretion) to determine whether the patient should permanently discontinue study drug or withhold study drug until toxicity resolves to Grade 1 or lower, then resume study drug at a dose corresponding to a reduction of one dose level.

A study schema for the dose-escalation stage is displayed in Figure 1.

Figure 1 Study Schema: Dose-Escalation Stage

DLT = dose-limiting toxicity.

Note: All patients will receive cobimetinib orally once daily on Days 1–21 of each 28-day cycle. Dose escalation for suspension will proceed in the same way after MTD of tablets has been established, starting at one dose level below the determined MTD or MAD of the tablets, and allowing for enrollment of patients 6 months to 6 years of age as permitted in Section 3.1.1.2.

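### Table 2 draws the permanent-stop line for bleeding in the head at the undefined word cerebral, while Section 5.1.2.1 draws it at intracranial; read literally, the two differ for a Grade 2 bleed such as a subdural.

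*Combined protocol and SAP*

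**What the plan says.** Section 5.1.2.1 (Hemorrhage Events) gives two instructions. For bleeds outside the skull: "For Grade 2 extracranial hemorrhagic events, investigator should not administer study drug until toxicity resolves to Grade" 1 or lower. For hemorrhage of Grade 3 or higher, "or for any intracranial hemorrhage, study drug should be permanently discontinued". The second carries no grade limit for intracranial bleeds.

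The same section also points elsewhere: "Instructions for dose modification for hemorrhage events are included in" Table 2. It adds that dose reductions and discontinuations are to follow that table.

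Section 5.1.1 introduces the table: "Guidelines for managing specific adverse events are provided in" Table 2. Its hemorrhage entry has three rows:
- "Cerebral hemorrhage (all grades": stop permanently.
- "Grade 2 hemorrhage (excluding cerebral hemorrhage": interrupt until Grade 1 or lower, then contact the Medical Monitor before any restart, with the caution "Do not resume cobimetinib without approval of Medical Monitor and careful benefit-risk assessment".
- Grade 3 or higher: stop permanently.

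After a dose-limiting toxicity (DLT), Section 3.1.1 says: "The investigator should use guidance in Section 5.1.1 and Table 2". Where the guidance is silent, it leaves the choice between a permanent stop and a resumption one dose level lower to the investigator. The DLT list in Section 3.1.1.1 uses intracranial, at any grade. The list of adverse events of special interest in Section 5.2.3 uses cerebral. The protocol neither defines cerebral nor equates it with intracranial.

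**The concern.** A reader who goes to Table 2, as the protocol directs, meets a different word at the point where a permanent stop parts from a possible restart. Intracranial takes in bleeding anywhere inside the skull. Cerebral can be read more narrowly, and a subdural bleed is the plainest example of one that is intracranial without being cerebral.

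What is at stake is whether a child who has bled inside the skull may receive the drug again. The trial admits patients with central nervous system gliomas, diffuse intrinsic pontine glioma and atypical teratoid/rhabdoid tumor. Section 5.1.2.1 lists hemorrhage among the important identified risks of cobimetinib. Table 2 itself acknowledges that there are no data on whether modifying the dose is effective for hemorrhage. The rule should therefore read the same wherever an investigator or the Medical Monitor looks it up.

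**Working it through.** No arithmetic applies, and the plan gives no figure to reproduce. The check sets the two rules side by side.

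**Inputs.** The permanent-stop and hold rules in Section 5.1.2.1; the three hemorrhage rows of Table 2, with actions paired to rows in the order printed; the post-DLT instruction in Section 3.1.1; the DLT definition in Section 3.1.1.1. Because cerebral is not defined, Table 2 is read in two ways.

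| Event | Section 5.1.2.1 | Table 2, cerebral taken as intracranial | Table 2, cerebral taken literally |
|---|---|---|---|
| Cerebral, any grade | Permanent stop | Permanent stop | Permanent stop |
| Intracranial but not cerebral, Grade 1 | Permanent stop | Permanent stop | No hemorrhage row |
| Intracranial but not cerebral, Grade 2 | Permanent stop | Permanent stop | Hold; restart possible with approval |
| Intracranial but not cerebral, Grade 3 or higher | Permanent stop | Permanent stop | Permanent stop |
| Extracranial, Grade 2 | Hold until Grade 1 or lower | Hold; restart possible with approval | Hold; restart possible with approval |

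**Step 1: where the rules part.** With cerebral taken as intracranial, the table and the section agree on every line. Taken literally, they differ on two lines, both for bleeds that are intracranial but not cerebral. At Grade 2, Table 2 permits what Section 5.1.2.1 forbids. At Grade 1, Table 2 has no hemorrhage row.

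**Step 2: which text governs.** No order of precedence is stated. Section 5.1.2.1 contains the stricter sentence but also defers to Table 2. Section 3.1.1 names Section 5.1.1 and Table 2 and does not name Section 5.1.2.1. Section 5.1 applies the guidelines in both the dose-escalation and expansion stages. The cross-references thus lead to the place with the narrower word.

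**Step 3: Grade 1 after a DLT.** In dose escalation, an intracranial bleed of any grade that is related or possibly related to drug is a DLT if it falls in Days 1–28 of Cycle 1. The investigator is then sent to Table 2. On the literal reading there is no row, so the investigator-discretion clause in Section 3.1.1 applies, and one of its two options is resuming at a lower dose. The Medical Monitor approval in Table 2 belongs to the Grade 2 row and does not reach this case.

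**Step 4: DLT counting.** Section 3.1.1.1 already uses intracranial at any grade. The wording of Table 2 therefore does not alter which bleeds count as DLTs.

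**The case against.** The strongest reply is that there is no real contradiction. Table 2 never orders a restart; it permits one, behind approval and a benefit-risk assessment. Stopping drug permanently satisfies both texts for every intracranial bleed, and restarting would breach an express sentence of the protocol. The structures also match tier for tier: extracranial in Section 5.1.2.1 sits where the exclusion of cerebral bleeds sits in Table 2. That section moves between cerebral, intracerebral and intracranial without marking a difference, and it treats the table as carrying its own rule.

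Most of this stands. The likely intent is that cerebral means intracranial, and a careful reader of both places would stop drug. There are further safeguards: hemorrhage of any grade except Grade 1 epistaxis is reported to the Sponsor within 24 hours, a patient with a DLT may not continue at full dose, and Section 5.1 says that the guidelines do not replace clinical judgment. What remains is that the intended meaning must be inferred. Medical Monitor approval does not settle which text governs, and it does not cover the Grade 1 case.

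A reader might go further in several ways that the documents do not support:
- *That the protocol directs re-treatment after an intracranial bleed.* It does not. The restart is conditional, and Section 5.1.2.1 forbids it.
- *That a Grade 1 bleed is left without any instruction.* Section 5.1.2.1 covers it; the gap is in Table 2 and in the route that Section 3.1.1 takes.
- *That the eligibility waiver for a recent asymptomatic central nervous system bleed makes such bleeds likely on treatment.* That criterion concerns entry, not management on drug, and Section 9.2 says that requests to waive eligibility criteria are not allowed. It is not relied on here.

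**Conclusion.** The point holds as a terminology inconsistency in an operative safety rule, with a limited consequence. The direct conflict is confined to Grade 2 bleeds that are intracranial but not cerebral. A related gap exists at Grade 1, where Table 2 has no row. At Grade 3 and above there is no difference.

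The conclusion rests on one assumption: that some investigator or Medical Monitor could read cerebral more narrowly than intracranial. If both always treat the words as synonyms, or always apply Section 5.1.2.1 alongside the table, the difference disappears.

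The documents do not show how often such a bleed would occur, so no frequency is claimed. Nor is a number of affected bleeding sites, since that would depend on which sites and readings one chose. A reader might also infer that the maximum tolerated dose could be affected; the DLT definition already uses the broader word, so no such effect is claimed. No endpoint, sample size or estimate changes. The change is still worth making, because it concerns whether drug may be given again after bleeding inside the skull, and the table is where the protocol sends people for the answer.

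**What to change.** In Table 2, relabel the first hemorrhage row *Intracranial hemorrhage (all grades)* and, in the Grade 2 row, change the exclusion to *excluding intracranial hemorrhage*. This matches Sections 5.1.2.1 and 3.1.1.1. Every intracranial bleed, Grades 1 and 2 included, then falls in the permanent-stop row, and Grade 2 extracranial bleeds keep the hold rule. The discretion clause in Section 3.1.1 no longer comes into play for these events.

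The special-interest list in Section 5.2.3 needs no change, because it already covers hemorrhage of any grade apart from Grade 1 epistaxis. In the same edit, Section 5.1.2.1 could correct its one reference that places Table 2 in Section 5.1.2; the table is in Section 5.1.1.

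The cost is two wording edits at the next amendment, with no added patients, visits or procedures.
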